### **III. SESSION 2. Practical resources and addressing new questions**

**Goal:** win trust and address immediate reactions/needs

**When?** During week 3 (*or week 4 if intervention is 3 months long*)

**Setting:** In-person ideally or over Zoom if preferred by the patient. Involves the patient and their caregiver.

**Duration:** 60-120 minutes

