#### **C. Palliative care (continued)**

#### **D. PRACTICAL SKILLS/WORKSHOPS**

1. Tips to reduce the time burden (too many MDs?/appts?) with MyChart or other tools
  2. Complementary therapies: massage, aromatherapy, music, art therapy, etc....
  3. Cooking classes and recipes.
  4. Physical activities: yoga, Tai chi or other easy exercises
- 

**IV. TELEHEALTH VISIT** with resource person of choice (facilitated by CHWs).

**Goal:** provide customized resources based on patients' needs

**When?** During week 3-6

**Setting:** In groups (online or in-person?) patients and caregiver(s)

**Duration:** 1 hr

(Optional) According to patients' desires or interests, information can be provided about end of life plans (community resources, estate planning, finances, funeral homes, funeral services, etc..)

---

**V. FOLLOW-UP PERIOD** – patients and caregivers (*if program lasts 3 months*)

**Goal:** CHWs weekly calls providing help to problem solve & provide support and if needed can meet the patient in person.

[figure not shown]
**When?** During weeks 7 to 12

**Setting:** Telephone and if needed virtual or in-person.

**Duration:** varie

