## **17. DATA COLLECTION AND MANAGEMENT RESPONSIBILITIES**

### **Data Collection**

We will collect baseline demographics data (age, gender, race/ethnicity, date of diagnosis, stage of diagnosis, and treatments) from the patient's chart. We will also administer the following surveys before the first study visit, at 4 weeks and 3 months.

- FACT-HEP (measures HRQoL) - 30 questions
- NCCN-FACT Hepatobiliary-Pancreatic Symptom Index – 18 questions
- Palliative Care Attitude Survey (PCAS-9) – 9 questions
- ACP (Advanced care planning engagement) survey – 4 questions
- Acceptability of intervention measure (AIM) survey – 4 questions
- Technology Comfort (our survey) – 12 questions

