## **18. STATISTICAL ANALYSIS**

**Quantitative Analysis.** We will first determine the distribution of the primary and secondary outcomes for the usual care and CHW arms by using a Shapiro–Wilk test to assess the normality for these outcomes. Then accordingly we will report either a mean (standard deviation) or a median (95% confidence interval) for both arms for the NCCN-FACT Hepatobiliary-Pancreatic Symptom Index and FACT-Hep scores and then use the standard deviation or variance for the power analyses for a larger definitive subsequent RCT. We will also use a t-test and Wilcoxon rank-sum test to compare the differences between these measures between the two groups at different time points. To assess a preliminary pre/post effect, we will compare survey data between baseline and 4 weeks using generalized linear models to compute contrasts for continuous variables from the FACT-Hep subscores, NCCN-FCAT HPBSI, PCAS-9, and ACP Engagement Survey scores.

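### The only modelled contrast ends at 4 weeks, although the surveys are repeated at 3 months and the CHW programme, whose length is left open, can run to week 12

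*Protocol*

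**What the plan says.** **Analysis (section 18).** The model is introduced with the words "To assess a preliminary pre/post effect", and the sentence goes on: "we will compare survey data between baseline and 4 weeks", with contrasts taken from generalized linear models. It covers the FACT-Hep subscores, the symptom index, PCAS-9 and the ACP survey. A separate sentence plans a t-test and a Wilcoxon rank-sum test to "compare the differences between these measures between the two groups at different time points". The SD or variance of the two main scales is to feed the power calculation of a later definitive trial; no visit is attached to it.

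**Surveys (section 17, Data Collection).** "We will also administer the following surveys before the first study visit, at 4 weeks and 3 months".

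**Primary endpoint (section 7c).** Change in the symptom index and in FACT-Hep, with no time point.

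**Programme (Pancreatic Cancer CHW Intervention, parts I to V).** The presurvey and digital introduction come within a week of diagnosis and Session 1 in week 2. Session 2 is in week 3, "or week 4 if intervention is 3 months long". The telehealth visit is in weeks 3 to 6. The weekly CHW calls are scheduled "During weeks 7 to 12", under a heading qualified by "if program lasts 3 months".

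**The concern.** The one analysis whose window the protocol fixes looks at the early visit only. If the programme runs for 3 months, that contrast estimates the effect of its opening part, before any of the weekly calls. A null result there could not be read as failure of the whole programme, and the later survey, already scheduled, would get no modelled estimate.

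Two open points make this worse. First, there are two follow-up visits, the between-group tests may be run at either, and neither is named as primary, so the more favourable one could be stressed after the data are seen. Second, the two programme lengths give the 3-month survey different meanings: it falls at the end of the programme in one version and about six weeks after it (12 − 6) in the other. Sections 5, 6 and 18 give the pilot's purpose as a preliminary effect estimate and a variance for planning a larger trial. Both need a stated visit and a single intervention behind them.

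**Working it through.** The protocol gives no figure to reproduce here: the 60 patients are stated without alpha, power, effect size or SD. The check is a count on the protocol's own schedule.

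**Inputs** (CHW Intervention, parts I to V)
- Introduction: 1 contact, 1 hour, within 7 days of diagnosis
- Session 1: 1 contact, 1 to 2 hours, week 2
- Session 2: 1 contact, 1 to 2 hours, week 3 or week 4
- Telehealth visit: 1 contact, 1 hour, weeks 3 to 6
- Weekly calls, 3-month version only: weeks 7 to 12, so 12 − 7 + 1 = 6 calls of unstated duration

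**Assumptions.** The shorter version ends when the telehealth window closes, in week 6. Session 2 has taken place by the 4-week survey. The text messages are left out because no stop date is given for them.

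**Share inside the modelled window**

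| | 3-month version | Shorter version |
|---|---|---|
| Calendar weeks | 4/12 = 33% | 4/6 = 67% |
| Total contacts | 1 + 2 + 1 + 6 = 10 | 1 + 2 + 1 = 4 |
| Contacts, telehealth still to come | 3/10 = 30% | 3/4 = 75% |
| Contacts, telehealth done | 4/10 = 40% | 4/4 = 100% |
| Weekly calls | 0/6 | none planned |

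**By hours.** Let s be the length of a session (1 or 2 hours), t = 1 if telehealth is done by 4 weeks and 0 if not, and c the length of a call. The share is (1 + 2s + t)/(2 + 2s + 6c).
- Shorter version (c = 0): from 3/4 = 75% (s = 1, t = 0) to 6/6 = 100% (s = 2, t = 1).
- 3-month version, with c assumed because the protocol leaves it open:
  - 15 minutes: 3/5.5 = 55% to 6/7.5 = 80%
  - 30 minutes: 3/7 = 43% to 6/9 = 67%
  - 60 minutes: 3/10 = 30% to 6/12 = 50%

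**After the fix.** Adding the 3-month survey to the model brings coverage to 12 of 12 weeks in the longer version and to the whole programme in the shorter one. No sample-size figure changes.

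**The case against.** Several stronger readings are tempting, and the protocol does not support them.

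- A reader might infer that the efficacy analysis as a whole stops at 4 weeks. It does not. The model is labelled a preliminary pre/post look, and the between-arm tests are a separate sentence that can take in 3 months.
- A reader might infer that the planning SD will be the 4-week SD. Section 18 sets no such limit, and a 3-month SD can be obtained as written. What is missing is a statement of which one will be used.
- A reader might say that the model precedes most of the programme. By weeks and contacts that is true only of the 3-month version. Both long sessions are due by week 3 or 4, and by hours the answer depends on how long the calls last.
- A reader might count only two of ten contacts by 4 weeks, placing a week-4 Session 2 after the survey. The protocol does not say what the 4 weeks are counted from. Counted from a baseline in week 1, the survey falls at or after the end of week 4; counted from Session 1 in week 2, it falls around week 6. In either case an on-schedule Session 2 has taken place.
- A reader might call the intervention undefined. Its session content is set out at length; only the overall length and the week of Session 2 are conditional.

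An early contrast also has a rationale in the document. Section 7a reports that 72% of a prior cohort had a clinically significant fall in quality-of-life domains at 30 days, and describes unmet symptom needs before oncology care begins. Finally, model detail commonly sits in a statistical analysis plan, and none is shown here.

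These arguments narrow the point but do not remove it. The protocol itself states the model's window, and that window leaves out a survey it schedules. What the intervention arm receives is not something an analysis plan can settle. On any of these origins for the 4 weeks, the calls in weeks 7 to 12 come later.

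**Conclusion.** The concern holds in a limited form. The only modelled contrast uses baseline and 4 weeks, while the surveys continue to 3 months and the programme may continue to week 12. In the 3-month version 4 of 12 weeks, about 3 to 4 of 10 contacts and none of 6 calls fall inside the modelled window; in the shorter version 3 to 4 of 4 contacts do. The gap is therefore large in one version and small in the other, and the protocol does not say which version will be run. The counts rest on Session 2 being done by the 4-week survey and on the shorter version ending in week 6. The missing primary time point and the conditional programme length stand without any assumption. This should be corrected, but it does not invalidate the pilot, because the data needed are already scheduled.

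**What to change.** 1. Before the first randomisation, reconcile the conditional wording in parts III and V of the CHW Intervention into one programme version, with one length and one week for Session 2, applied to every intervention patient. Which version is for the investigators to decide.
2. In section 18, extend the model to both scheduled follow-up visits with an arm-by-visit term, and report the between-arm effect and the SD at 4 weeks and at 3 months. State what the 4 weeks and 3 months are counted from.
3. Once the length is settled, name in section 7c which visit is primary for the effect estimate and for the planning SD, before any outcome data are seen. The choice depends on step 1: without it, the 3-month survey could be either the end of the programme or a follow-up some six weeks later.

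The cost is protocol wording. No visits, surveys or patients are added. The downside is more missing data at 3 months than at 4 weeks in this population; fitting both visits in one model handles part of that, not all of it.
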